6.6 Dose Modification

See Section 4.1 for information on dose modification. No dose modifications are allowed except for the one described in section 4.1 (Cohort C), if recommended by the DMC.

6.7 Intervention after the End of the Study

No further intervention is planned after the end of the study. No long-term effects are expected that would need any additional care or intervention. Participants who completed or prematurely discontinued the study will discontinue study intervention and will switch to the most appropriate available treatment at the physician's discretion.

7. Discontinuation of Study Intervention and Participant Discontinuation/Withdrawal

7.1 Discontinuation of Study intervention

In rare instances, it may be necessary for a participant to permanently discontinue (definitive discontinuation) study intervention. If study intervention is definitively discontinued, the participant will remain in the study to be evaluated for key outcome events, as described in Section 7.1.1, unless the participant withdraws from the study. See the SoA (Section 1.3) for data to be collected at the time of discontinuation of study intervention and follow-up, and for any further evaluations that need to be completed.

Abnormal liver function

Discontinuation of study intervention for abnormal liver function should be considered by the investigator when a participant meets one of the conditions outlined in Section 8.3.8.2 or if the investigator believes that it is in best interest of the participant.

Cardiac changes

If a clinically significant finding is identified in ECG (including, but not limited to changes from baseline in QT interval corrected using Bazett's formula [QTcB] or Fridericia's formula [QTcF]) after enrollment, the investigator or qualified designee will determine if the participant can continue in the study and if any change in participant management is needed. This review of the ECG printed at the time of collection must be documented. Any new clinically relevant finding should be reported as an AE.

07 JUL 2021 Page: 39 of 90

See the SoA (Section 1.3) for data to be collected at the time of intervention discontinuation and follow-up and for any further evaluations that need to be completed.

7.1.1 Events Requiring Definitive Discontinuation of Study Intervention

A participant must permanently discontinue study intervention for any of the following:

- The participant becomes pregnant. The pregnancy will be reported per reporting procedures in Section 8.3.5.
- The participant is unwilling to continue study intervention.
- The participant experiences an AE (including clinically significant bleeding [Sections 8.2.1 and 8.3]) that in the judgment of the investigator necessitates permanent discontinuation of study intervention.
- Requires surgery that in the judgment of the investigator necessitates permanent discontinuation of study intervention.
- The participant develops laboratory test abnormalities that meet any of the stopping rules listed in Section 8.3.8.1.2 and 8.3.8.2.2.
- The participant is no longer on maintenance hemodialysis (including hemodiafiltration) for a minimum of 9 hours per week, including a change in dialysis modality (e.g. peritoneal dialysis) or renal transplantation.
- The participant moves their dialysis care to a different hemodialysis facility where the study team cannot continue to follow the participant.
- The participant begins treatment with a disallowed concomitant medication and the study intervention is interrupted for >56 days, as described in Section 6.5.

When a study participant discontinues the study intervention early:

- During the main treatment period, the participant should conduct Visit 22 four weeks after the last dose of study intervention
- During the extended treatment period, the participant will conduct Visit 28 four weeks after the last dose of study intervention
- In both cases, the participant will then enter the 16-week follow-up period, giving a total of 20 weeks of follow-up from the last dose of study intervention.

If the participant moves their dialysis care to a different hemodialysis facility where the study team cannot follow the participant, all efforts should be made to conduct the evaluation and post-treatment follow-up visits in person to complete all study procedures. If in-person visits by the participant are impossible, limited remote contact visits (e.g. phone) may be conducted recording as much information as possible for eCRF entry. The reason for discontinuation of study intervention must be recorded in the eCRF and source documentation.

7.1.2 Temporary Discontinuation

The investigator may temporarily discontinue study intervention for an AE, bleeding event, temporary use of prohibited concomitant medication, for a surgery or other invasive procedure, or any other reason not listed as reasons for definitive discontinuation of study intervention (Section 7.1.1) or withdrawal from the study (Section 7.2). Examples of these are

07 JUL 2021 Page: 40 of 90

(but not limited to): if any exclusion criterion applies during treatment, if a significant violation of the protocol occurs, as defined by the sponsor.

If the discontinuation remains necessary > 56 days from the last dose, the participant will be permanently discontinued from study intervention.

7.1.3 Rechallenge

Participants who permanently discontinue the study intervention must not be re-challenged (i.e., must not restart study intervention). Participants who temporarily discontinue study intervention (for less than 57 days) (Section 7.1.2) may be rechallenged after careful assessment by the investigator of the potential risks.

7.2 Participant Discontinuation/Withdrawal from the Study

- A participant may withdraw from the study at any time at his/her own request, or may be withdrawn at any time at the discretion of the investigator for safety, behavioral, compliance, or administrative reasons. This is expected to be uncommon. If the participant withdraws consent, or the investigator withdraws the participant, the reason for withdrawal should be recorded on the eCRF.
- Additional reasons for withdrawal from the study:
 - Death of participant, in which case only relevant eCRF pages will be completed (e.g.- AEs [including the cause of death] and concomitant medications up to death, vital status, etc).
 - The participant signs-off dialysis without expected return of life-sustaining kidney function or without transferring to an alternative form of renal-replacement therapy, the reason for withdrawal of renal replacement therapy should be recorded on the eCRF.
 - o If a stopping rule is met (see Sections 8.3.8.1.2, 8.2.1.1 and 8.3.8.2.2) during the screening period, the participant should be screen-failed.
- At the time of discontinuing from the study, if possible, an early termination visit should be conducted, as shown in the SoA. See SoA for data to be collected at the time of study discontinuation and follow-up and for any further evaluations that need to be completed.
- The participant will be permanently discontinued both from the study intervention and from the study at that time.
- If the participant withdraws consent for disclosure of future information, the sponsor may retain and continue to use any data collected before such a withdrawal of consent.

If a participant is permanently discontinued/withdrawn from the study, the Early Termination Visit in the SoA will be conducted immediately. All study outcomes will be censored at Early Termination.

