7.3 Lost to Follow Up

A participant will be considered lost to follow-up if he or she repeatedly fails to return for scheduled visits and is unable to be contacted by the study site.

The following actions must be taken if a participant fails to return to the clinic for a required study visit:

07 JUL 2021 Page: 41 of 90

- The site must attempt to contact the participant and reschedule the missed visit as soon as possible and counsel the participant on the importance of maintaining the assigned visit schedule and ascertain whether or not the participant wishes to and/or should continue in the study.
- Before a participant is deemed lost to follow up, the investigator or designee must make every effort to regain contact with the participant (where possible, 3 telephone calls and, if necessary, a certified letter to the participant's last known mailing address or local equivalent methods). These contact attempts should be documented in the participant's medical record.
- Should the participant continue to be unreachable, he/she will be considered to have withdrawn from the study.

The investigator should make all efforts to determine the survival (vital status) of any participant who would otherwise be lost to follow-up during the treatment period or post-treatment follow-up period, whether by direct contact or indirect contact with a reliable source (family-member, health-care provider, etc). The survival status will be recorded in the eCRF. If no survival status is known, the contact attempt will be recorded.

8. Study Assessments and Procedures

- Study procedures and their timing are summarized in the SoA. Protocol waivers or exemptions are not allowed.
- Immediate safety concerns should be discussed with the sponsor immediately upon occurrence or awareness to determine if the participant should continue or discontinue study intervention.
- Adherence to the study design requirements, including those specified in the SoA, is essential and required for study conduct.
- All screening evaluations must be completed and reviewed to confirm that potential participants meet all eligibility criteria. The investigator will maintain a screening log to record details of all participants screened and to confirm eligibility or record reasons for screening failure, as applicable.

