6.2.1.1 Other Exploratory Efficacy Analyses

Efficacy Analysis by Component

The single components of the main efficacy variable will be analyzed in a similar way to the main efficacy analysis in section 6.2.1.

Analysis of Death Events

The main efficacy analysis will be repeated for overall death and for its components (Death due to MI, stroke, pulmonary embolism (PE) and systemic embolism (SE), CV death, Non-CV death, Undetermined death, and other reasons).

Pre-Treatment Efficacy Summary

Pre-treatment events between randomization and first dose of study intervention will be listed.

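### Protocol 7.2 withdraws participants who stop dialysis for good and censors their outcomes without any withdrawal of consent, so deaths that follow have no routine route into the planned death, TEAE and competing-risk analyses

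*Protocol*

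**What the plan says.** Protocol 7.2 gives additional reasons for withdrawal from the study. One is: "The participant signs-off dialysis without expected return of life-sustaining kidney function or without transferring to an alternative form of renal-replacement therapy". The consequences follow in the same section: "The participant will be permanently discontinued both from the study intervention and from the study at that time", an Early Termination Visit is held at once, and "All study outcomes will be censored at Early Termination".

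Protocol 7.1.1 lists events that require a permanent stop of study intervention. One is: "The participant is no longer on maintenance hemodialysis (including hemodiafiltration) for a minimum of 9 hours per week, including a change in dialysis modality" or renal transplantation. These participants have Visit 22 or Visit 28 four weeks after the last dose. Then: "In both cases, the participant will then enter the 16-week follow-up period, giving a total of 20 weeks of follow-up from the last dose".

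Protocol 7.3 provides a search for vital status: "The investigator should make all efforts to determine the survival (vital status) of any participant who would otherwise be lost to follow-up". It is written for loss to follow-up, not for withdrawal under 7.2.

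On the analysis side, SAP 6.2.1.1 states: "The main efficacy analysis will be repeated for overall death and for its components". SAP 6.4.2 counts overall TEAEs to 20 weeks after the last dose. SAP 6.2.2.2 and 6.4.1.1 use death as a competing event.

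**The concern.** A participant who stops dialysis permanently is also no longer on maintenance hemodialysis, so both sections describe the same person. One section keeps that person under observation for 20 weeks after the last dose; the other ends observation that day. Protocol 7.2 itself calls the missing kidney function life-sustaining, so death soon afterwards is plausible. Censoring at sign-off would then remove people at the point where their risk of death is highest, and censoring of that kind is plausibly informative about death.

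What is at stake is the completeness of the death and late-safety data in a study with 72 treated participants planned per analysis group, whose primary analysis feeds Phase 3 dose selection (Protocol 4.1).

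**Working it through.** The plan gives no rate of dialysis sign-off and no expected number of deaths, so there is no stated figure to reproduce. The check compares the texts and then illustrates the scale.

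**1. Do both rules apply to one participant?** The 7.1.1 trigger is being off maintenance hemodialysis; modality change and transplantation are given as inclusions, not as a closed list. There is no exception for sign-off and no pointer to 7.2. The two sections overlap as written.

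**2. Could a death after sign-off still enter the data?**
- Protocol 7.3: the vital-status search covers loss to follow-up only.
- Protocol 8.3.1: after discharge from the study, a death is notified only if the investigator learns of it and judges it related.
- Protocol 8.3.3: SAEs already reported are followed to resolution or stabilization, so a fatal outcome of a known SAE may reach the safety record.
- Protocol 8.3.10: all deaths after randomization go to the CIAC, but this presupposes that the site knows of the death and is still collecting data.
- Even when a death is known, 7.2 censors all study outcomes at Early Termination.
- Sign-off is not a named intercurrent event in Protocol 9.4.1.3, Protocol 9.4.2 or SAP 6.4.1, and the SAP does not say how to handle it.

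**3. How much observation is lost?** Up to 28 days on treatment plus 16 x 7 = 112 days of follow-up, or 140 days after the last dose.

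**4. Which analyses are touched?**
- Overall death and its components (SAP 6.2.1.1), and the death component of the efficacy composite (SAP 6.2.1).
- TEAEs to 20 weeks after the last dose (SAP 6.4.2).
- Competing-risk analyses (SAP 6.2.2.2 and 6.4.1.1): a death that should enter as a competing event, or as the event of interest, enters as censoring.
- The primary bleeding proportion: only new bleeds between Early Termination and last dose + 28 days. The participant stays in the denominator as a non-event.

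**5. Scale, under assumptions.** Inputs: 40% five-year survival on hemodialysis (Protocol 2.2.1); 72 participants per group (Protocol 9.2: 72 active per cohort, and 3 x 24 = 72 pooled placebo); constant hazard (assumed).
- Hazard = -ln(0.40)/5 = 0.183 per year.
- 24 weeks: 72 x (1 - exp(-0.183 x 24/52.18)) = 5.8 deaths.
- 40 weeks: 72 x (1 - exp(-0.183 x 40/52.18)) = 9.4 deaths.

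Forty weeks is the main period plus 16 weeks of follow-up. The 20 weeks in 7.1.1 run from the last dose, and their first four weeks fall inside the 24-week main period, so 24 and 20 are not added. Participants who complete the whole extension are observed for about 64 weeks.

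The share of deaths preceded by sign-off is not in the documents. At an assumed 10% to 25%:
- 0.10 x 9.4 = 0.9 to 0.25 x 9.4 = 2.4 deaths per group over 40 weeks.

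Effect on a reported proportion (exact 95% intervals): if 4 of 72 deaths are counted, that is 5.6% (1.5 to 13.6); with two more after sign-off it is 6 of 72, or 8.3% (3.1 to 17.3). For the primary endpoint, one missed new bleed would move an assumed 4/72 (5.6%) to 5/72 (6.9%).

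How often this arises is also an assumption. If 1%, 2% or 5% of participants sign off, that is 0.7, 1.4 or 3.6 per group of 72, and the chance of at least one in a group, 1 - (1 - r)^72, is 0.515, 0.767 or 0.975.

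**The case against.** The strongest reply is that 7.2 is a deliberate, specific exception to a general rule. Protocol 7.1 keeps discontinued participants in the study unless they withdraw from it, 7.2 names sign-off as a withdrawal reason, and the amendment summary records that a paragraph on sign-off was taken out of 7.1.1 as not belonging there. That is a fair reading of intent. It reduces the textual conflict to a missing exception or cross-reference, but it does not restore the deaths that the SAP plans to analyze.

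Several stronger inferences are tempting and are not supported.

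- **That a stroke or major bleed leading to sign-off is lost.** It precedes Early Termination and is already counted. The composite is analyzed as participants with an event and as time to first event, so only the separate death component, or a first event that is itself the death, could change. The bleeding tables in Protocol 9.4.2 have no fatal category, so a major bleed that later proves fatal alters no planned bleeding count.
- **That sign-off is commonly caused by the study outcomes, so the loss differs by arm.** The documents say nothing about why participants sign off. Differential loss is possible but not shown.
- **That the SAP's statement on independent censoring is thereby broken for the primary analysis.** That sentence in SAP 6.4.1.1 concerns exploratory cause-specific Cox models, where death and the end of exposure at last dose + 28 days are competing events, so the gap there is at most 28 days. The primary analysis is a descriptive proportion over all treated participants.
- **That every such death goes uncounted.** Protocol 8.3.1 and 8.3.3 leave partial routes for related deaths and for known SAEs.
- **That 7.1.1 already allows remote contact for this group.** That provision is written only for a move to another dialysis facility.

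It also stands that the study has no planned hypothesis test according to Protocol 9.1, and that the death analyses are exploratory.

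**Conclusion.** The point holds as a gap in data collection and analysis. Followed as written, the plan stops observing participants who sign off dialysis although consent has not been withdrawn, has no routine means of learning whether they died, and censors the death even if it is known. The main effect is on overall death, the death component of the efficacy composite, the 20-week TEAE summaries (a secondary endpoint) and death as a competing event. The effect on the primary bleeding proportion is small.

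The illustrative size is about 0.9 to 2.4 censored deaths per group of 72 over 40 weeks. It rests on a constant hazard from the 40% five-year figure and on an assumed 10% to 25% share preceded by sign-off. The true number is probably lower, because Protocol 5.2 excludes short life expectancy, active malignancy requiring treatment, advanced heart failure, and recent bleeding or thromboembolism. That death follows soon after sign-off is an inference from the protocol's own description of the lost function, not a figure it gives.

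This is worth correcting because it is cheap and the groups are small; it does not undermine the primary result.

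**What to change.** The change concerns data collection and analysis only, not clinical care.

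1. Reconcile Protocol 7.1.1 and 7.2 so that, unless consent is withdrawn, participants who sign off dialysis continue to have vital status, SAEs, outcome events and CIAC-adjudicated cause of death collected to 20 weeks after the last dose. Add the cross-reference that is now missing.
2. Extend to them the remote-contact provision that 7.1.1 now gives only for facility transfers.
3. Limit the rule that censors all study outcomes at Early Termination to withdrawal of consent.
4. State in the SAP how sign-off is handled, and count these deaths in the death, TEAE and competing-risk analyses.

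The cost is a protocol wording change, a new remote-contact provision, and a small number of phone or record contacts for few participants.

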7.3 Lost to Follow Up

A participant will be considered lost to follow-up if he or she repeatedly fails to return for scheduled visits and is unable to be contacted by the study site.

The following actions must be taken if a participant fails to return to the clinic for a required study visit:

07 JUL 2021 Page: 41 of 90

- The site must attempt to contact the participant and reschedule the missed visit as soon as possible and counsel the participant on the importance of maintaining the assigned visit schedule and ascertain whether or not the participant wishes to and/or should continue in the study.
- Before a participant is deemed lost to follow up, the investigator or designee must make every effort to regain contact with the participant (where possible, 3 telephone calls and, if necessary, a certified letter to the participant's last known mailing address or local equivalent methods). These contact attempts should be documented in the participant's medical record.
- Should the participant continue to be unreachable, he/she will be considered to have withdrawn from the study.

The investigator should make all efforts to determine the survival (vital status) of any participant who would otherwise be lost to follow-up during the treatment period or post-treatment follow-up period, whether by direct contact or indirect contact with a reliable source (family-member, health-care provider, etc). The survival status will be recorded in the eCRF. If no survival status is known, the contact attempt will be recorded.

8. Study Assessments and Procedures

- Study procedures and their timing are summarized in the SoA. Protocol waivers or exemptions are not allowed.
- Immediate safety concerns should be discussed with the sponsor immediately upon occurrence or awareness to determine if the participant should continue or discontinue study intervention.
- Adherence to the study design requirements, including those specified in the SoA, is essential and required for study conduct.
- All screening evaluations must be completed and reviewed to confirm that potential participants meet all eligibility criteria. The investigator will maintain a screening log to record details of all participants screened and to confirm eligibility or record reasons for screening failure, as applicable.
- Procedures conducted as part of the participant's routine clinical management (e.g., blood count) and obtained before signing of the ICF may be utilized for screening or baseline purposes provided the procedures met the protocol-specified criteria and were performed within the time frame defined in the SoA.
- If deemed necessary for an individual participant, the investigator or designee, at his/her discretion, may arrange visits in addition to the scheduled study visits. Unscheduled study visits will be documented in the eCRF.

8.1 Efficacy Assessments

The following efficacy outcomes will be assessed by the blinded CIAC in accordance with the pre-specified endpoint criteria in the adjudication charter:

- Death due to MI, stroke, PE or SE
- Non-fatal MI
- Non-fatal stroke

07 JUL 2021 Page: 42 of 90

- Major amputation of vascular etiology
- Acute limb ischemia (new onset ischemia or worsening or pre-existing ischemia)
- Venous thromboembolism
- Thrombosis of the arterio-venous grafts or fistulas

All deaths and events suspected to be related to cardiovascular disease, or other arterial or venous thrombosis events (including arterio-venous access thrombosis), but not limited to these, will be reported as an AE or SAE as per adverse event reporting procedure in Section 8.3. Additionally, the event will be triggered, within the eCRF, for adjudication by the CIAC. Details for the adjudication process are described in the adjudication charter.

